Thirty-eight individuals with aMCI will be enrolled in the 3-day interleaved TBS-fMRI study. Participants will be randomly assigned into one of the two TBS groups: active TBS or sham TBS (Figure 1). Participants will receive 3 TBS sessions on day 2 with each TBS session separated by 60 minutes to maximize the TBS effect^{5,6}. Participants in the active TBS group will receive 3 excitatory TBS sessions (the 3 yellow ovals in Figure 1). Participants in the sham TBS group will undergo a procedure identical to the active TBS except that no TBS will be provided (the 3 white ovals in Figure 1). Research participants and outcome assessors will be blinded for participants' allocated group. Outcome measures assessing memory function, hippocampal functional connectivity, and hippocampal activation during a memory task will be acquired on day 1 (baseline), day 2 (immediate effect), and day 3 (lasting effect). We hypothesize that active spaced TBS will enhance memory function, strengthen hippocampal functional connectivity, and increase hippocampal activation compared to the sham TBS immediately and 24 hours after the last TBS session.

Outcome measures

Accuracy of the face-name associative memory (FNAME) task, resting-state hippocampal functional connectivity, and hippocampal activation pattern will be the primary outcome measures. Participants will perform the FNAME task, which was adapted from previous paradigm^{7,8}, inside the MRI scanner. The FNAME task consists of both encoding and retrieval phases (Figure 4). During the encoding phase, participants will be instructed to remember the name that goes with each face and make a subjective decision as to how well each name fits the corresponding face (a strategy designed to augment associative encoding)⁹. Encoding phase will be divided across 4 functional runs, each consisting of 16 face-name pairs (display duration = 5.5 sec for each pair), interspersed with fixation trials (duration = 0.5-12.5 sec), yielding a total of 64 face-name pairs. Following encoding with a 5-min break, participants will

be presented with 3 types of face-name pairs (correct face-name pairs, incorrect face-name pairs, or new face-name pairs) inside the MRI scanner during the retrieval phase. There are 4 functional runs, each consisting of 10 correct, 6 incorrect, and 6 new face-name pairs interspersed with fixation trials, yielding a total of 88

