face-name pairs. Accuracy will be measured as the number of right responses (e.g., Figure 4 face-name pairs B-D) relative to the total number of face-name pairs shown during the retrieval phase. We created 8 versions of the face-name tasks. Our pilot data from 20 healthy adults indicated excellent parallel-forms reliability across the 8 test versions (ICC = 0.93, 95%CI = [0.88, 0.97]). The administration order of different versions will be randomized across the participants. The score of the FNAME task has been found to be correlated with beta amyloid burden⁷, reduced hippocampal volume, and APOE4 carrier status in cognitively normal older adults¹⁰. The FNAME task is sensitive to longitudinal clinical decline in MCI¹¹ and in those at genetic risk for AD¹²⁻¹⁴.

Statistical design and analysis

This study employs a parallel group design with 2 groups (active TBS and sham TBS) and 3 primary data collection time points (day1, day 2, and day 3). Participants will be randomized to one of the 2 groups using a randomization scheme stratified on age (50-65 vs. 66-80) and sex. For the accuracy of the FNAME task, a linear mixed effects model will be fit to the accuracy scores from the FNAME task to look at the change in accuracy over time for both the active and sham TBS groups. The model will include fixed predictors for time (3 levels: day 1, day 2, and day 3), group (2 levels: active TBS and sham TBS), their interaction, age, sex, and education. A

random intercept per participant will be included to account for the potential correlation among data from the same participant.

1. Petersen, R. C. *et al.* Mild cognitive impairment: a concept in evolution. *J Intern Med* **275**, 214-228 (2014). <https://doi.org/10.1111/joim.12190>
2. Jak, A. J. *et al.* Neuropsychological Criteria for Mild Cognitive Impairment and Dementia Risk in the Framingham Heart Study. *J Int Neuropsychol Soc* **22**, 937-943 (2016). <https://doi.org/10.1017/S1355617716000199>
3. Weintraub, S. *et al.* Version 3 of the Alzheimer Disease Centers' Neuropsychological Test Battery in the Uniform Data Set (UDS). *Alzheimer Dis Assoc Disord* (2017). <https://doi.org/10.1097/WAD.0000000000000223>
4. Shirk, S. D. *et al.* A web-based normative calculator for the uniform data set (UDS) neuropsychological test battery. *Alzheimer's research & therapy* **3**, 32 (2011). <https://doi.org/10.1186/alzrt94>

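### FNAME accuracy: a shared day-1 mean with an unstructured covariance would use the baseline better than the planned mixed model, at little cost; the gain depends on an unknown between-day correlation and on stable variances

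*Combined protocol and SAP*

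**What the plan says.** Trial design makes day 1 the baseline and places all stimulation afterwards: "Participants will receive 3 TBS sessions on day 2 with each TBS session separated by 60 minutes". Day 2 is to show the immediate effect and day 3 the lasting one.

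Statistical design and analysis fits a linear mixed model to FNAME accuracy, and states its aim as "to look at the change in accuracy over time for both the active and sham TBS groups". On the fixed effects, the wording of that section is: "The model will include fixed predictors for time (3 levels: day 1, day 2, and day 3), group". The list then goes on to "their interaction, age, sex, and education". For the covariance, a "random intercept per participant will be included to account for the potential correlation among data from the same participant".

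Allocation: "Participants will be randomized to one of the 2 groups using a randomization scheme stratified on age (50-65 vs. 66-80) and sex". Baseline FNAME is not a stratification factor.

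The documents do not name the coefficient or contrast that measures the treatment effect. They do not set the day-1 means equal, adjust for day-1 accuracy, or give an alternative covariance. The one reliability figure is under Outcome measures: "Our pilot data from 20 healthy adults indicated excellent parallel-forms reliability across the 8 test versions (ICC = 0.93, 95%CI = [0.88, 0.97".

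**The concern.** A day-1 score taken before treatment cannot respond to it, and randomisation makes the two day-1 means equal in expectation. With a group main effect and a full interaction, the model still estimates a separate day-1 difference. If the group-by-day-2 and group-by-day-3 terms are the treatment effects, each one with complete data is exactly the difference between arms in mean change from day 1. Age, sex and education are constant within a person, so they do not sharpen it.

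Two things are at stake. The first is precision: the change score subtracts all of baseline, whatever weight the data support, in a trial of 38 people. The second is the standard error. A random intercept implies one common variance of the difference between any two days. If days 1 and 3 are less alike than adjacent days, the day-3 test uses a standard error that is too small and the day-2 test one that is too large.

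**Working it through.** **Inputs.** From the documents: 38 participants, two randomised arms, one pre-treatment and two post-treatment days, random intercept. Assumed: 19 per arm, complete data, two-sided 5% tests. ρ is the between-day correlation left after age, sex and education; it is not given, so a range is shown. The sample size of 38 cannot be reproduced, because no power, effect size or SD is stated. The comparison below does not depend on how it was chosen.

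**Step 1: large-sample variance, equal variances across days.** With n per arm:

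- Plan: (2/n) × 2σ²(1−ρ)
- Shared day-1 mean: (2/n) × σ²(1−ρ²)
- Ratio: (1−ρ²) / [2(1−ρ)] = (1+ρ)/2

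**Step 2: small-sample cost.** Estimating the baseline weight multiplies the variance by 1 + 1/(38−4) = 35/34. Break-even on variance is ρ = 68/35 − 1 = 0.94. Degrees of freedom fall from 72 (36 × 2 within-person) to about 36. The last two columns come from simulation with the three covariates in the model but uninformative, Kenward-Roger tests and 20,000 data sets per setting, averaged over the day-2 and day-3 contrasts.

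| ρ | (1+ρ)/2 | × 35/34 | Simulated ratio | Power where plan has 80% |
|---|---|---|---|---|
| 0.5 | 0.75 | 0.772 | 0.790 | 87.4% |
| 0.7 | 0.85 | 0.875 | 0.885 | 83.3% |
| 0.8 | 0.90 | 0.926 | 0.937 | 81.4% |
| 0.88 | 0.94 | 0.968 | 0.972 | 80.0% |
| 0.93 | 0.965 | 0.993 | 0.995 | 78.9% |
| 0.97 | 0.985 | 1.014 | 1.015 | 78.7% |

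Break-even on power is at ρ of about 0.88. At 0.97 the exact calculation without covariates gives 78.3%.

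**Step 3: unequal variances.** Let post-treatment SD be k times baseline. The large-sample ratio becomes k²(1−ρ²) / (1 + k² − 2kρ). At ρ = 0.7:

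- k = 1.1: 1.21 × 0.51 / 0.67 = 0.921; × 35/34 = 0.95 (simulated 0.96)
- k = 1.2: 1.44 × 0.51 / 0.76 = 0.966; × 35/34 = 0.99 (simulated 1.00)

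Ratios of 0.96 and 1.00 with 36 df give 80.5% and 78.9% power, so the gain at moderate ρ has largely or wholly gone. Over the ρ values in the table, simulated ratios run from 0.85 to 1.03 at k = 1.1 and from 0.80 to 1.03 at k = 1.2. If the SD falls (k = 0.9), they are 0.70 to 0.85. A ratio of 1.03 with 36 df gives 77.7% power, a loss of 2.3 points.

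**Step 4: the covariance.** The random-intercept model estimates one residual variance, in effect the average of (1−correlation) over the three pairs of days. Suppose the day 1-day 3 correlation is 10% below the others, with ρ = 0.93:

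- Day 1-day 3: 1 − 0.837 = 0.163; each other pair: 0.07
- Average: (0.163 + 0.07 + 0.07)/3 = 0.101
- True over assumed variance: day 3, 0.163/0.101 = 1.61; day 2, 0.07/0.101 = 0.69

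The plan's simulated type I error is then about 12% on day 3 and 2% on day 2. With a 5% lower correlation the day-3 figure is about 9%. With 10% lower at ρ = 0.6 and 0.8 it is about 6% and 7-8%. The unstructured fit stays near 5%.

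**The case against.** The plan's contrast is legitimate, and the only reliability figure in the documents points to no gain. Across the ICC's interval of 0.88 to 0.97, power under the alternative is 80 to 79%, against 80% for the plan. That stands if the figure carries over. It is, however, parallel-forms reliability in 20 healthy adults, not day-to-day correlation in aMCI after covariates.

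A reader might infer that 0.93 describes the mean of eight versions, so that one version has 0.93/(8 − 7 × 0.93) = 0.62 and the gain is sizeable. The documents do not say so. F-based limits at 0.93 are 0.878-0.967 for one version, which round to the reported interval, and 0.872-0.968 for a mean of eight, which do not. The mean-of-eight reading fits only if the unrounded ICC is about 0.932-0.935. The form is unsettled and leans, if anything, towards one version.

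Test noise gives no firm answer either. With 88 scored pairs ("each consisting of 10 correct, 6 incorrect, and 6 new face-name pairs interspersed with fixation trials, yielding a total of 88"), binomial SD is about 5 points at an assumed 60-70% accuracy. Assumed true-score SDs of 8-15 points then give ρ of 0.70-0.90, but those SDs are not in the documents.

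It is also fair to say that the unstructured covariance is not strictly required. If variances and correlations are equal across days, a shared mean with the random intercept holds type I error at 0.048-0.052 and has slightly more power (89.1% at ρ = 0.5, 81.2% at 0.93). Nothing in the documents says that SDs will grow or correlations decay. Nothing assures the opposite, and if post-treatment SD is 1.1 or 1.2 times baseline, that version's type I error rises to 0.056-0.060 or 0.062-0.075.

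**Conclusion.** This is a cheap improvement for FNAME accuracy, not an error. A reader might infer that the planned analysis is biased or that the trial forfeits a fifth of its precision. The documents support neither. The change contrast is unbiased, and a gain of 21-23% of variance needs ρ near 0.5 and roughly equal variances across days.

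Under equal variances the shared mean saves about 12% of variance at ρ = 0.7, 6-7% at 0.8 and practically nothing from 0.93 up. If post-treatment SD is 10-20% larger than baseline, the saving at ρ = 0.7 falls to between 5% and nothing.

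The covariance is a separate matter and counts even at high ρ: modest decay between days 1 and 3 would make the plan's lasting-effect test anti-conservative. That decay is an assumption.

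All sizes assume 19 per arm, complete data, and the group-by-day terms as the treatment effects. The plan does not name that contrast, and it should do so whichever model is kept.

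**What to change.** In Statistical design and analysis, for FNAME accuracy:

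- Drop the group main effect so that both arms share one day-1 mean. Keep day, group-by-day-2, group-by-day-3, age, sex and education.
- Name the group-by-day-2 and group-by-day-3 coefficients as the treatment effects.
- Replace the random intercept with an unstructured within-person covariance, with small-sample degrees of freedom (for example Kenward-Roger).

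This takes a sentence or two of wording and no new data. About 1.1 power points of the statistical cost come from the covariance alone: the plan's own contrast with 36 df has 78.9% power.

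If the sponsor holds aMCI data showing ρ of about 0.9 or more, keeping the free day-1 difference is reasonable, but the contrast should still be named and the covariance reconsidered. Separate ANCOVAs for each day on day-1 score, age, sex and education are not an equivalent substitute. At this size their variance ratio is (1+ρ)/2 × 35/31, which exceeds 1 above ρ = 62/35 − 1 = 0.77.
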